### 4.10.3 Secondary Efficacy Analysis

The secondary outcome measures are described in [Section 3.2.3](#). All secondary endpoints analyses will be performed on the Intention-to-Treat Analysis Set. The following secondary endpoint analyses will be repeated on the PPS:

- Proportion of participants who develop ASNV determined by the investigator at Week 24.
- Proportion of participants who develop CI-DME at Week 24.
- Change in DRSS steps is defined as DR worsening or improving by 1, 2, or  $\geq 3$  steps.
- Proportion of participants with mild PDR (DRSS score 61B) at baseline who regress to NPDR (DRSS score  $\leq 53$ ) by Week 24
- Mean and median change in BCVA (ETDRS letters) from baseline to Week 24.
- Lines gained/lost in BCVA ( $\pm 5, 10, \text{ and } 15$  ETDRS letters) at Week 24.
- Mean and median change in CST from baseline to Week 24.
- Proportion of participants who met the objective rescue criteria as defined in protocol section 2.14.9.
- Time to meet the objective rescue therapy criteria.
- Proportion of participants who develop VTC at Week 24

Continuous variable and changes from baseline will be summarized at each visit by treatment using descriptive statistics. Categorical variables will be summarized at each visit by treatment using frequencies and percentages.

The secondary endpoints involving proportions of participants will be analyzed using the same approach (MH test) as described for the primary efficacy analysis and based on the ITT Analysis set.

The categorical secondary endpoints will be compared using a proportional odds model with covariates for treatment group and the randomization stratification factor. If the assumption of proportional odds is rejected, a different analysis approach, such as a rank-based ANCOVA, will be

considered. The rank-based ANCOVA will be a two-sided test and a two-sided p-value will be presented.

The time to event secondary endpoints will be defined as time to first development of an event and will be estimated based on the Kaplan-Meier method, along with a 90% confidence interval. Analyses will be based on observed data, where participants who receive rescue medication will be censored at the start of rescue medication. A stratified log-rank test adjusting for the randomization stratification factor will be performed, to compare the combined vehicle control with each treatment group. Additionally, a stratified Cox proportional hazards model adjusting for the randomization stratification factor will be employed to estimate the hazards ratio between the combined vehicle control and each treatment group.

Continuous secondary endpoints involving change from BL to Week 24 will be analyzed using an analysis of covariance (ANCOVA) model with BL measurement of the variable as a covariate and treatment group and the randomization stratification factor as fixed factors. As a sensitivity analysis of the continuous secondary endpoints involving change from BL to Week 24, a rank-based ANCOVA model will be employed. The pair-wise comparisons of each OTT166 dose group versus combined vehicle control will be done in the ANCOVA model. Two-sided 90% confidence intervals for the difference of each OTT166 dose group minus combined vehicle control will be calculated.

The specific reasons for meeting rescue criteria as described in protocol section 2.14.9 will also be summarized using number and percentage by treatment group.

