### 3.2.3 Secondary Endpoints

The secondary outcome measures are as follows:

- Proportion of participants developing worse than mild PDR (DRSS 65 and above) at Week 24.
- Proportion of participants who develop ASNV determined by the investigator at Week 24.
- Time to development of PDR worse than mild (DRSS 65 and above).
- Proportion of participants who develop CI-DME at Week 24.
  - CI-DME is defined as the presence of fluid in the central subfield in participants who have no fluid at baseline or CST > 325 μm.
- Time to development of CI-DME.
- Proportion of participants with change in DRSS steps at Week 24 compared to baseline.
  - Change in DRSS steps is defined as DR worsening or improving by 1, 2, or ≥3 steps.

- Proportion of participants with mild PDR (DRSS score 61B) at baseline who regress to NPDR (DRSS score  $\leq 53$ ) by Week 24.
- Mean and median change in BCVA (ETDRS letters) from baseline to Week 24.
- Lines gained/lost in BCVA ( $\pm 5, 10, \text{ and } 15$  ETDRS letters) at Week 24.
- Mean and median change in Area Under the Curve (AUC) for change in BCVA from baseline to Week 24.
  - AUC from baseline to 24 weeks will be calculated by the linear trapezoidal method:

$$AUC_{(t_i - t_{i-1})} = (t_i - t_{i-1}) * \frac{f(t_i) + f(t_{i-1})}{2}$$

$$AUC_{(24-0)} = \sum_{t_0=0}^{24} AUC_{(t_i - t_{i-1})}$$

where,  $t_i = \#$  of weeks since baseline, which may include 0, 4, 8, 12, 16, 20, 24 according to schedule of visits, if available.

- Mean and median change in CST from baseline to Week 24.
- AUC for change in CST from baseline to Week 24.
- Proportion of participants who met the objective rescue criteria as defined in protocol section 2.14.9.
- Time to meet the objective rescue therapy criteria as defined in protocol section 2.14.9.
- Proportion of participants who develop VTC at Week 24
- Time to development of PDR worse than mild (DRSS 65 and above) or CI-DME

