## 4.10 Efficacy Evaluation

### 4.10.1 Analysis and Data Conventions

This study is designed to evaluate the superiority of two doses of OTT166 (5 mg/day and 10 mg/day) compared to vehicle control for the treatment of DR. For each dose within each endpoint, the null hypothesis is that there is no difference between OTT166 and vehicle control or the difference is in the direction of inferiority of OTT166, and the alternative hypothesis is that there is a difference between OTT166 and vehicle control in the direction of superiority of OTT166.

All statistical tests will be one-sided and will be performed at the 5% level of significance, unless otherwise stated. The vehicle control group will be combined for all efficacy analyses and two-sided 90% confidence intervals will be presented. A comparison between the two control groups will be performed for the primary endpoint to confirm the groups are comparable.

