#### 4.10.2 Primary Efficacy Analysis

The primary efficacy outcome measure of the study will be the proportion of participants who have improved by  $\geq 2$  steps from BL DRSS at Week 24. DRSS score levels will be recoded into 12 steps, provided by WRC.

Comparison of the primary endpoint will be made between each dose group and the combined vehicle control group using Mantel-Haenszel (MH) test of the difference in two proportions stratified by the randomization stratification factor (BL DRSS score 47 or 53 or 61B). The estimated MH risk difference will be summarized along with the two-sided 90% CI using MH stratum weights and the Sato variance estimator.

The primary efficacy analysis will be performed on the ITT Analysis Set, while the PPS will be used as a supplementary analysis. ICEs and missing data will be handled as described in [Section 4.10.1.2](#).

In order to assess the robustness of the study conclusions to the choice of imputation method, the following sensitivity analyses will be performed on the ITT Analysis Set and PPS for the primary endpoint:

- An observed case analysis where only observed responses will be used for analysis.  
Observed data after initiation of rescue medication will be set to missing.
- A LOCF analysis where missing post-baseline responses will be imputed using the LOCF procedure.  
Measurements after rescue will be imputed using the last observation prior to rescue treatment; a non-response will be imputed if no post-baseline measurements are available.

A supplementary analysis will be performed on the ITT Analysis Set and PPS for the primary endpoint to assess the time to improvement of  $\geq 2$  steps improvement from BL in DRSS score. Analyses will be based on observed data, where participants who receive rescue medication will be censored at the start of rescue medication (unless improvement of  $\geq 2$  steps improvement from BL in DRSS score is achieved prior to starting rescue medication). This analysis will be presented based on the Kaplan-Meier method, along with a 90% confidence interval. A stratified log-rank test adjusting for the randomization stratification factor will be performed, to compare the combined vehicle control with each treatment group. Additionally, a stratified Cox proportional hazards model adjusting for the randomization stratification factor will be employed to estimate the hazards ratio between the combined vehicle control and each treatment group.

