#### 4.13 Determination of Sample Size

The study will enroll approximately 210 participants, 70 participants in each OTT166 treatment group and 35 participants per group into each matching vehicle control group and allowing for around 5% study attrition, this will ensure at least 66 participants per treatment group and combined vehicle control group.

For the primary endpoint of improvement by at least 2 steps from baseline on the DRSS at Week 24, completing 66 participants per group (active treatment BID, active treatment QID, combined vehicle control) through Week 24 will yield at least 90% power to demonstrate that the active treatment is superior to placebo using a 1-sided alpha of 0.05, provided that the true treatment effect (active treatment efficacy rate minus control efficacy rate) is at least 0.20 and the control efficacy rate is at most 0.06.

The sample size calculation was computed in nQuery 8.7 using a Chi square test for two proportions (continuity corrected).

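### SAP 4.10.3 names no sparse-event method: for ASNV and DRSS 65 and above, the Sato 90% interval is 0 to 0 with no events and covers about 50% to 75% when true rates differ and the higher is about 2% or less.

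*SAP*

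**What the plan says.** For the primary endpoint, SAP 4.10.2 specifies: "The estimated MH risk difference will be summarized along with the two-sided 90% CI using MH stratum weights and the Sato variance estimator". The strata are the three DRSS levels used at randomisation. SAP 4.10.3 extends the method: "The secondary endpoints involving proportions of participants will be analyzed using the same approach (MH test) as described for the primary efficacy analysis". Protocol 2.21.2.2 says the same.

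SAP 4.10.1 sets the error rate and interval level for all of these comparisons: "All statistical tests will be one-sided and will be performed at the 5% level of significance", and "The vehicle control group will be combined for all efficacy analyses and two-sided 90% confidence intervals will be presented".

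Two of the secondary proportions in SAP 3.2.3 are harm outcomes: "Proportion of participants developing worse than mild PDR (DRSS 65 and above) at Week 24" and "Proportion of participants who develop ASNV determined by the investigator at Week 24". Missing values for secondary proportions are handled as for the primary endpoint, by multiple imputation with intercurrent-event rules (SAP 4.10.1.2).

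Neither document offers an exact, score-based or zero-event alternative for a proportion with few events. SAP 4.10.3 does give a fallback for the proportional odds model, so a conditional rule would suit the section.

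**The concern.** The Sato variance is built from the observed event counts. It suits an endpoint planned at 6% against 26%. If an endpoint has no events, or one, the variance is zero or close to it, and the interval understates what is unknown.

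ASNV is the likeliest case. Current ASNV in the study eye is an exclusion, the investigator must judge that laser or anti-VEGF injection can be safely deferred for at least 6 months, mild PDR is capped at 20%, and follow-up is 24 weeks. DRSS 65 and above may be more frequent.

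A secondary objective asks whether OTT166 prevents or delays vision-threatening complications. An interval of 0 to 0 from 70 participants per group would present that question as settled, when the data could not exclude a difference of several points in either direction.

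**Working it through.** **Inputs.** SAP 4.13: "The study will enroll approximately 210 participants, 70 participants in each OTT166 treatment group and 35 participants per group" of matching vehicle. The two vehicle groups are combined, so each comparison is 70 vs 70, with 66 completers planned per group. The 61B stratum is capped at 20%, that is 0.20 × 70 = 14. The split between 47 and 53 is not given; 28/28/14 is assumed. True event rates are not given; 0% to 10% was examined.

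**The plan's own figure.** For 6% vs 26%, one-sided 5%, continuity-corrected chi-square, the required size is 66 per group and power at 66 is 90.3%. SAP 4.13 is reproduced. It concerns the primary endpoint only.

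**Sato formula.** For each stratum, with a of n1 events on OTT166, b of n0 on vehicle, and N = n1 + n0:
- W = n1·n0/N
- P = [n1²·b − n0²·a + n1·n0·(n0 − n1)/2]/N²
- Q = [a(n0 − b) + b(n1 − a)]/(2N)
- d = Σ[(a·n0 − b·n1)/N]/ΣW
- Var = (d·ΣP + ΣQ)/(ΣW)²

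With 28/28/14 in each group, W = 14, 14 and 7, so ΣW = 35.

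**No events in either group.** d = 0 and every Q = 0, so Var = 0 and the interval is 0 to 0. The test statistic is 0/0.

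The unstratified Miettinen-Nurminen interval for 0/70 vs 0/70 solves δ²/[δ(1 − δ)/70 × 140/139] = 1.645² = 2.706. Then 69.5·δ/(1 − δ) = 2.706, and δ = 2.706/72.206 = 0.0375. The interval is −3.7 to +3.7 points (±3.8 when stratified 28/28/14).

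**One event against none, in a stratum of 28.** d = (28/56)/35 = 0.0143, P = −784/3136 = −0.25 and Q = 28/112 = 0.25. Var = (−0.0036 + 0.25)/1225 = 0.000201, SE = 0.0142. The Sato interval is −0.9 to 3.8 points. The score interval is −2.3 to 6.2 (stratified −2.4 to 6.2).

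**Chance of a zero-width interval, complete data.** At a common rate of 0.5%, 0.995^140 = 49.6%. At 1% it is 24.5%, and at 2% it is 5.9%. Both OTT166 groups share one vehicle group. With q the chance of no event in 70, the chance that at least one of the two comparisons collapses is q·[1 − (1 − q)²], which gives 64%, 37% and 10%.

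**Coverage of the nominal 90% interval.** Exact binomial enumeration at 70 vs 70, one stratum:

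| True rates, OTT166 / vehicle | Sato | Score |
|---|---|---|
| 0% / 1% | 50.0% | 99.5% |
| 0.5% / 1% | 62.4% | 99.4% |
| 1% / 2% | 72.8% | 93.5% |
| 0% / 2% | 74.4% | 98.7% |
| 0.5% / 2% | 74.7% | 95.1% |
| 1% / 3% | 84.2% | 94.9% |
| 1% / 5% | 83.2% | 88.5% |
| 2.5% / 5% | 90.8% | 87.8% |
| 5% / 10% | 89.3% | 89.9% |
| 0.5% / 0.5% | 99.2% | 99.2% |
| 1% / 1% | 96.7% | 96.7% |
| 2% / 2% | 91.0% | 91.0% |
| 5% / 5% | 88.0% | 88.0% |

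The first row can be checked by hand. At 0%/1% the vehicle group has no event with probability 0.99^70 = 49.5%. The interval is then 0 to 0 and misses the true −1 point, so coverage cannot exceed 50.5%.

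A three-stratum simulation agrees with the Sato column within 0.3 points. At 66 per group, Sato coverage is up to 2 points lower when rates differ and within 0.6 points when they are equal.

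**False claim of benefit.** At equal true rates of 0.5%, 1%, 2%, 3% and 5%, the Sato interval wrongly excludes zero in favour of OTT166 in 0.4%, 1.7%, 4.5%, 5.8% and 6.0% of trials, against a nominal 5%.

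**The case against.** **Low rates alone do not break the interval.** A reader might infer that Sato undercovers badly whenever events are rare. It does not: with equal rates of 2% or less, coverage is 91% to 99%, because 0 to 0 contains the true difference of zero. This stands and limits the point to unequal rates.

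**Rarity is assumed.** The documents give no rate. Worsening to DRSS 65 or higher and development of ASNV are also rescue criteria (SAP 4.8), and secondary proportions inherit the primary intercurrent-event rules. The SAP does not say whether the inherited non-response rule makes a rescued participant an event or a non-event on a harm endpoint. If an event, these endpoints need not be rare. This stands as a condition on the finding.

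**Multiple imputation may give some width.** The collapse and the coverages are complete-data results. Imputed events could produce a non-zero pooled standard error, so the zero-width frequencies are not established for the planned analysis. This stands. It is no remedy, though: the imputation model has only treatment and stratum as covariates, and with no observed event any width would come from the model rather than the data.

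**The consequence is limited.** The hypotheses are one-sided superiority and no equivalence claim is planned. These are unadjusted secondary endpoints in Phase 2, and counts by group are reported. A reader might infer that rare events inflate false claims of efficacy; the figures above show at most about 6%. Nor do the documents show that CI-DME, VTC or rescue is rare; VTC includes CI-DME and cannot be rarer than it.

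**A score interval is not a complete cure.** It over-covers at the lowest rates, matches Sato at 5%/5%, and supplies no standard error for MIANALYZE to pool. Its test is also undefined with no events in either group. All of this stands and shapes the fix.

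**Conclusion.** The concern holds in limited form. The plan carries the Sato interval to two harm endpoints that may be sparse and names no alternative. With no events in either group and complete data, the interval is 0 to 0 where about ±3.7 points would be honest. When the true rates differ and the higher is about 2% or less, coverage is about 50% to 75%. When the higher rate is 3% to 10% it is about 83% to 91%, at worst a modest shortfall.

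The result rests on 70 per group, complete data, and event rates that are assumed. The damage is to the precision reported for vision-threatening complications; no large false-positive risk follows. The primary analysis is unaffected. This should be corrected before database lock, but it does not threaten the trial's main conclusion.

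**What to change.** In SAP 4.10.3, add a rule for ASNV and DRSS 65 and above, and for any other secondary proportion that turns out sparse:

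- When either group in a comparison has fewer than 5 observed events before imputation, report the stratified Miettinen-Nurminen (or stratified Newcombe) 90% interval on the observed data, with the intercurrent-event rule applied, in place of the Sato interval. Choose one of the two now.
- State in SAP 4.10.1.2 whether a rescued participant counts as an event or a non-event for each harm endpoint; the count cannot be fixed without it.
- Report no p-value when neither group has an event.
- Keep Mantel-Haenszel/Sato with multiple imputation for the primary endpoint and for proportions that are not sparse.

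Counting observed events before imputation gives one count per group, and using observed data avoids pooling a score interval across imputations. The threshold of 5 is a convention; coverage of the switching rule itself was not simulated.

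The cost is a short SAP change and one extra analysis step. The intervals become wider and somewhat conservative at the lowest rates, and the sparse-event interval does not use imputed data.

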#### 4.10.4 Exploratory Analysis

Exploratory imaging outcome measures are described in [Section 3.2.4](#).

- All exploratory endpoint analyses will be performed on the Intention-to-Treat Analysis Set and will be based on observed data, where observed data after the initiation of rescue medication will be set to missing unless specified otherwise. The following exploratory endpoint analyses will be repeated on the PPS:
  - Change in MV from baseline to Week 24 for 1, 3, and 6 mm regions.
  - Change in area of retinal non-perfusion from baseline to Week 24 seen on widefield FA.
  - Proportion of participants with intact FAZ seen on widefield FA at Week 24.

The exploratory endpoints involving proportions of participants will be analyzed using the same approach (MH test) as described for the primary efficacy analysis if not specified otherwise.

The time to event exploratory endpoints will be estimated based on the Kaplan-Meier method, along with a 90% confidence interval. A stratified log-rank test adjusting for the randomization stratification factor will be performed, to compare the combined vehicle control with each treatment group. Additionally, a stratified Cox proportional hazards model adjusting for the randomization stratification factor will be employed to estimate the hazards ratio between the combined vehicle control and each treatment group.

Continuous exploratory endpoints involving change from BL will be analyzed using an ANCOVA model with BL measurement of the variable as a covariate and treatment group and the randomization stratification factor as fixed factors. The pair-wise comparisons of each OTT166 dose group versus combined vehicle control will be done in the ANCOVA model. Two-sided 90% confidence intervals for the difference of each OTT166 dose group minus combined vehicle control will be calculated.

Within participant treatment effects will also be assessed for the primary endpoint (DRSS step change of  $\geq 2$  steps) and key secondary endpoints (BCVA change, CST change, and development of CI-DME). Differences in outcomes from screening to Week 24 between eyes for participants in the two active treatment groups (OTT166 5 mg/day, OTT166 10 mg/day) will be compared using an appropriate paired data analysis: McNemar's test for dichotomous data and either a paired t-test or a Wilcoxon signed-rank test for continuous outcome data (changes from baseline). Data for eyes that were treated with anti-VEGF and/or laser will be imputed with LOCF from the time of starting treatment with anti-VEGF and/or laser. The earliest concomitant medication in the fellow eye with ATC4CD="SL01A" will be considered for anti-VEGF treatment in the fellow eye. Additionally, the first ocular concomitant procedure in the fellow eye will be considered for laser treatment. The ocular concomitant procedures will be reviewed and confirmed by the clinical team.

Associations between baseline covariates and compliance may be assessed graphically: monthly compliance may be presented as a series of boxplots for each baseline subgroup, by treatment group and overall, allowing for the observation of compliance trends within or between groups.

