
Designation of Study Eye:
 
Only one eye will be designated as the study eye in every participant. For participants who meet eligibility criteria in both eyes during the screening phase, the eye with the higher reading center confirmed DRSS should be selected. If both eyes have the same score, the eye with the clearest lens and ocular media will be selected. If there is no objective basis for selecting the study eye, factors such as ocular dominance (better focus ability), other ocular pathology, and participant preference should be considered in making the selection. The final selection will be done by the Investigator in discussion with the participant at baseline and must not be changed during the course of the study.
 
The non-study eye is eligible for treatment according to the standard of care treatments through the duration of the study.
	

Study procedures/assessments:
 
Assessments will be performed monthly during each clinic visit unless indicated otherwise in the Schedule of Activities (SoA), and include the following:
 
 • Adverse event recording • Review of concomitant medications • Vital signs • Physical examination (Screening Visit only) • Laboratory testing (hematology, blood chemistry, urinalysis, and HbA1c) • Pregnancy testing (as applicable) • BCVA (ETDRS) • Slit-lamp bio-microscopy • Ocular surface health [fluorescein stain of the cornea] • IOP • Indirect ophthalmoscopy/dilated fundus examination • Spectral domain OCT (SD-OCT) (central subfield thickness, macular volume, foveal contour) at every visit 	

- 7-field or 4-wide field color fundus photography at every visit [optional wide-field if available]
- DRSS scoring, based on 7-field or 4-wide field photos by the PI at baseline to confirm eligibility
- Fluorescein angiography (FA) (wide field if available) at baseline and end of study
- OCTA if available (for exploratory endpoints) at baseline and end of study
- Rescue therapy initiation, per alignment between Investigator and Medical Monitor
- HbA1c at screening and end of treatment
- Gonioscopy

Visit Timeline:

Screening – Visit 1; Baseline (BL) – Visit 2; Week 4 – Visit 3; Week 8 – Visit 4; Week 12 – Visit 5; Week 16 – Visit 6; Week 20 – Visit 7; Week 24 – Visit 8

Rescue Criteria:

Participants meeting any of the following criteria would qualify for rescue with anti-VEGF therapy and/or PRP laser after consultation with the Medical Monitor:

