2.13 Selection of the Study Eye

Only one eye will be designated as the study eye in each participant. For participants who meet eligibility criteria in both eyes during the screening phase, the eye with the higher reading center confirmed DRSS should be selected. If both eyes have the same score, the eye with the clearest lens and ocular media will be selected. If there is no objective basis for selecting the study eye, factors such as ocular dominance (better focus ability), other ocular pathology, and participant preference should be considered in making the selection. The final selection will be performed and documented by the investigator in discussion with the participant at BL and must not be changed during the study.

The non-study eye is eligible for treatment according to the standard of care treatments through the duration of the study.

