3.1.5 Committees Structure

3.1.5.1 Central Reading Center

The digital retinal images, OCT scans, fluorescence angiographies, and other images as applicable will be assessed by independent central reading centers. Details pertaining to each imaging technique are as follows:

- FP: DRS 4W/7M standard 2-step plus adjudication
- OCT: CI-DME, SRF/IRF, DRIL, TMV (1, 3, and 6mm)
- FA: We will grade ONLY study eye
- OCTA: vessel density, FAZ area, and nonperfusion

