### 4.2 General Presentation Considerations

‘Baseline’ is defined as the last available pre-treatment assessment for safety assessments. For DRSS score, the Baseline value is defined as the Screening/Visit 1 result. Pre-treatment values for DRSS were collected at the Screening/Visit 1 using fluorescein angiography in addition to fundus photography whereas Baseline/Visit 2 used fundus photography only. Participants were enrolled into the study and randomized to the study treatment based on the Screening/Visit 1 DRSS result. All other efficacy analyses that do not use DRSS score will use the last available pre-treatment assessment as Baseline. If an assessment is taken on the same day as first administration of study drug, it is eligible to be used as the Baseline value. This is considered acceptable as this measurement is still the best representation of the Baseline value of the given assessment since it is highly unlikely that the study drug could have an impact on any measurement in a short period of time.

‘End of Study’ is defined as the last available post-treatment assessment.

‘Study Day’ will be calculated relative to the date of randomization for untreated randomized participants and relative to the date of first dose for treated participants. If event is prior to the first dose, then study day is calculated as:

$$\text{Date of Event} - \text{Date of Day 1.}$$

If event is after the first dose, then study day is calculated as:

$$\text{Date of Event} - \text{Date of Day 1} + 1.$$

‘Study day 1’ is defined as the date of randomization for untreated randomized participants or the date of first dose for treated participants.

Time to event analyses will be calculated from Study Day 1, including time to DRSS-related endpoints comparing to the Baseline value. These analyses will consider only post-Baseline assessments. The Visit 2/Baseline visit will not be considered.

Duration of Treatment (days) will be calculated as:

$$\text{Last Date of Dose} - \text{First Date of Dose} + 1.$$

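### The study-eye versus fellow-eye comparison in the active arms (SAP 4.10.4) is called a treatment effect, but for DRSS the eyes would be expected to differ even if the drug did nothing

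*SAP*

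**What the plan says.** SAP 4.10.4 opens the analysis with "Within participant treatment effects will also be assessed for the primary endpoint" and extends it to BCVA change, CST change and development of CI-DME. The comparison is of "Differences in outcomes from screening to Week 24 between eyes for participants in the two active treatment groups". It uses McNemar's test for binary outcomes and a paired t-test or Wilcoxon signed-rank test for continuous ones. Eyes given anti-VEGF or laser have their last value carried forward from the start of that treatment. The vehicle groups do not enter. The section does not say whether the two active groups are pooled, whether McNemar's test is one- or two-sided, or whether it is exact or asymptotic.

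Three other places determine how the eyes differ:

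- **Selection.** Under Protocol 2.13, when both eyes qualify, "the eye with the higher reading center confirmed DRSS should be selected". Ties go first to media clarity: "If both eyes have the same score, the eye with the clearest lens and ocular media will be selected". The DRSS window of 47, 53 or 61B applies to the study eye; no limit is set for the fellow eye.
- **Baseline.** SAP 4.2: "For DRSS score, the Baseline value is defined as the Screening/Visit 1 result". This is the grade on which participants were enrolled.
- **Grading.** SAP 4.2 adds that "Pre-treatment values for DRSS were collected at the Screening/Visit 1 using fluorescein angiography in addition to fundus photography", while Protocol 3.1.5.1 says "FA: We will grade ONLY study eye".

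**The concern.** McNemar's null hypothesis is that the two eyes have equal response rates. That is the same as no drug effect only if the eyes would respond equally without the drug. Here one eye is chosen partly because its Screening reading was high, and improvement is then counted from that reading. Some of the high reading is grading error, which does not recur at Week 24, so the study eye tends to appear to improve. A fellow eye below the window lacks this selection; one above it may regress more.

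The two eyes may also have been graded on different evidence if angiography informed only the study eye's grade. The documents leave this open.

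The randomised comparison in SAP 4.10.2 does not depend on this analysis. What is at stake is interpretation. A favourable paired p-value on the primary outcome variable, labelled a treatment effect, could be read as corroboration in a study meant to support Phase 3 dose selection.

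**Working it through.** **1. The plan's own figure.** The documents give no figure for the between-eye analysis. The sample size in SAP 4.13 supplies the inputs: vehicle 0.06, active 0.06 + 0.20 = 0.26, one-sided 5%, 90% power, continuity-corrected chi-square.

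- Uncorrected n = [1.645 × √(2 × 0.16 × 0.84) + 1.282 × √(0.06 × 0.94 + 0.26 × 0.74)]² / 0.20² = 55.7.
- Corrected n = (55.7/4) × [1 + √(1 + 4/(55.7 × 0.20))]² = 65.3, so 66 per group.
- Power at 66 is 0.903. Allowing 5% attrition, 66/0.95 = 69.5, so 70.

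The plan's figure reproduces. Below, 66 pairs and a 6% no-drug rate are used; SAP 4.13 gives 6% as a ceiling.

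**2. What McNemar's test needs.** With study-eye rate p, fellow-eye rate q and independent responses, the discordant probabilities are p(1−q) and q(1−p), which differ by p−q. Enumerating the one-sided 5% test with p = 0.06 (sidedness assumed from SAP 4.10.1):

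| q | exact, 66 pairs | asymptotic, 66 pairs | exact, 132 pairs | asymptotic, 132 pairs |
|---|---|---|---|---|
| 0.06 | 0.019 | 0.050 | 0.030 | 0.050 |
| 0.03 | 0.086 | 0.198 | 0.217 | 0.324 |
| 0.02 | 0.141 | 0.309 | 0.378 | 0.524 |

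The error rate is at or below nominal when the no-drug rates are equal. Pooling the active arms (132 pairs) makes the inflation worse.

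**3. Does the design make the rates unequal?** Simulation with no drug effect. All of these are assumptions:

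- a 12-step order of 10, 20, 35, 43, 47, 53, 61, 65, 71, 75, 81, 85, with steps 5 to 7 eligible and 61B capped at 20%;
- bivariate normal true severity, rounded after grading error, with the same error in both eyes;
- the Protocol 2.13 selection rule, with ties broken at random;
- Screening grade as baseline, and response defined as at least 2 steps better.

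Central setting (mean step 5, SD 1.3, between-eye correlation 0.7), with grading error tuned to the stated study-eye rate:

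| Study-eye rate | Study minus fellow | Exact | Asymptotic | Exchangeable eyes (exact / asymptotic) |
|---|---|---|---|---|
| 6% | 3.2 points | 0.095 | 0.217 | 0.020 / 0.050 |
| 4% | 2.2 points | 0.042 | 0.172 | 0.013 / 0.050 |
| 2% | 1.1 points | 0.006 | 0.081 | 0.003 / 0.040 |

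A two-sided 5% test at the 6% rate gives 0.048 / 0.133.

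Moving the mean severity, still at 6%: mean step 4 gives 6.0% against 1.8% (0.157 / 0.341); mean step 6 gives 6.0% against 5.4% (0.026 / 0.066). Among pairs with both eyes eligible, the study eye is about twice as likely to improve at mean steps 4, 5 and 6 (about 5.3% v 2.5%, 5.7% v 2.7%, 6.3% v 3.1%).

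**4. What shrinks it.** Central setting at 6%:

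- 30% of eyes ineligible on non-DRSS grounds: 2.5 points, 0.066 / 0.156.
- A Visit 2 eligibility filter (the synopsis lists "DRSS scoring, based on 7-field or 4-wide field photos by the PI at baseline to confirm eligibility"): 1.8 points, 0.049 / 0.118.
- Both: 1.2 points, 0.037 / 0.089.

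**5. Full grid.** Mean step, correlation, spread or real change, response rate, ineligibility and the Visit 2 filter were crossed to give 432 settings. The gap runs from −1.8 to +5.0 points (median +1.0) and is positive in 346: 144 of 144 at mean step 4, 141 of 144 at step 5, 61 of 144 at step 6. The exact test exceeds 0.05 in 90 settings and the asymptotic test in 330. These counts describe the grid and are not probabilities.

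**6. The randomised contrast on the same kind of data.** Study-minus-fellow score, active against vehicle, 66 v 66, linear model with arm and stratum, one-sided 5%: rejection with no drug effect is 0.051 in the central setting and 0.045 to 0.058 over 47 settings.

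**The case against.** **It is exploratory.** No success or dose-selection rule uses it, and the same outcomes are already compared with randomised vehicle. This stands, and it limits the importance of the point. It does not make the label correct.

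**The inflation rests on unstated choices.** With the exact test the central setting stays at or below 5% at a 4% or 2% rate, and at 6% if the test is two-sided. This also stands. But the exact test is conservative with so few discordant pairs: 0.042 at the 4% rate compares with 0.013 for exchangeable eyes.

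**The step order is assumed.** SAP 4.10.2 says only that 12 steps come from the reading centre, and the severity table (Protocol Appendix 2) shows 71/75 as one row and lists 53E and 60 separately. With one extra step between 53 and 61 the central gap becomes 5.1 points (exact 0.236), and at mean step 6 it rises from 0.5 to 4.4. So the stated range is not a bound, although this alternative points further in the same direction.

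**The Visit 2 filter depends on coding.** Choosing the eye at Screening and then requiring the Visit 2 grade to be in the window gives 2.4 points and 0.064 / 0.152, not 1.8 and 0.049 / 0.118.

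**The angiography difference is not shown.** Protocol 2.16.2 assigns DRSS grading to photographs, and both eyes' Screening images serve eligibility. It is a query, not an established bias.

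**Fellow-eye standard of care and the carry-forward rule were not simulated.** True. Carry-forward addresses later treatment of an eye, not how the study eye was chosen.

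**Conclusion.** The concern holds. SAP 4.10.4 tests equality of the two eyes in treated participants only. For DRSS that is not a test of no drug effect, because selection and baseline use the same Screening grade. This follows from the documents without simulation.

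The likely direction favours the study eye, with moderate confidence: it is consistent where both eyes qualify, and uncertain or reversed if many fellow eyes are graded above the window. Confidence in the size is low. The 3.2-point gap at a 6% rate is one illustration; the documents give no grading error, between-eye correlation or bilateral-eligibility rate, and the effect of the media-clarity tie-break is unknown. No direction is claimed for BCVA, CST or CI-DME.

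This is a minor point about an exploratory analysis that is wrong as labelled. It does not touch the primary result.

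**What to change.** In SAP 4.10.4:

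- Compute the study-minus-fellow difference in the combined vehicle group as well. Make the inferential result each active arm minus combined vehicle in that difference, with a two-sided 90% interval, as the section already does for continuous exploratory endpoints.
- For DRSS response and CI-DME, score each pair +1, 0 or −1 and fit a linear model with arm and Screening DRSS stratum, using the model residual variance. For BCVA and CST, compare the paired difference by ANCOVA with the randomisation stratum.
- Keep the active-only McNemar and paired tests as descriptive, state their side and version, and drop the treatment-effect label.
- State whether the fellow eye's Screening and Week 24 DRSS grades used angiography, reconciling SAP 4.2 with Protocol 3.1.5.1.

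If the extra contrast is not wanted, relabelling the active-only result as descriptive is the minimum.

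The cost is wording and programming. Protocol 2.15.1 already schedules photographs and SD-OCT in both eyes at screening, baseline, Week 12 and Week 24 in every arm, and BCVA in both eyes at every visit. With 66 v 66 and equal variances, the interval is about √2 = 1.4 times as wide as the one-arm paired interval. In the central setting at 26% v 6%, with the fellow eye unaffected by the drug, simulated power is about 0.90, against 0.95 for comparing study eyes directly. The 0.95 comes from the same linear model without continuity correction; the formula in step 1 gives 0.939 uncorrected and 0.903 corrected.
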